7.4 International and Long-distance Subjects

Patients that are travelling internationally or more than 50 miles away from the NIH, at the discretion of the principal investigator, may have their schedules modified. The week 30 evaluation will be a required assessment. Thereafter, patients may be seen at either 6 week, 12 week, or 24 week intervals depending on the ease of travel, medical support systems at home, and the PIs recommendations. If feasible, some pulmonary function tests and laboratory data may be obtained from home medical facilities.

8.0 ASSESSMENT TOOLS and PROCEDURES

Other than the pre-study evaluations to determine eligibility/baseline status and subsequent PFTs used to guide therapy, patients will be able to refuse any radiologic test or bronchoscopy procedure unless clinically indicated.

8.1 Pulmonary Function tests

Spirometry measures how much and how quickly air is moved in and out of the lungs. For these tests, the subject breathes into a mouthpiece attached to a recording device (spirometer). The information collected by the spirometer may be printed out on a chart called a spirogram. The more common lung function values measured used to assess the subjects on this trial will include:

Forced vital capacity (FVC). This measures the amount of air you can exhale with force after you inhale as deeply as possible.

Forced expiratory volume (FEV). This measures the amount of air you can exhale with force in one breath. The amount of air you exhale may be measured at 1 second (FEV₁).

Peak expiratory flow (PEF). This measures how quickly you can exhale. It is usually measured at the same time as your forced vital capacity (FVC).

Total lung capacity (TLC). This measures the amount of air in your lungs after you inhale as in your lungs after a normal exhale (FRC) and the amount after you exhale with force (RV).

Maximum voluntary ventilation (MVV). This measures the greatest amount of air you can breathe in and out during one minute.

Exhaled Nitric Oxide measurement. This measures the amount of nitric oxide exhaled in your breathe after exhalation. This will be performed in a subset of subjects based on the availability of testing staff and scheduling.

Lung Volumes using Nitrogen Washout. This measures the total lung capacity and provides an estimate of residual volume of the lung.

Diffusing Capacity of the lungs for carbon monoxide (DLCO). This measures the ability of the lungs to transfer gas from inhaled air to the red blood cells in pulmonary capillaries.

Peak Flow Measurements: Patients will be given a home peak flow meter that will measure their peak flow and FEV1. The results will be recorded, and patients will be given a level below which, they should call the research team. Patients with a decline in peak flow of >20% compared to pretreatment baseline will be instructed to return to the NIH for formal pulmonary function testing. Subjects will be encouraged to perform peak flow testing daily, however, failure to perform peak flow measurements will not be considered a protocol deviation.

8.2 Bronchoscopy and bronchoalveolar lavage (BAL)

Bronchoalveolar lavage (BAL) is a medical procedure in which a bronchoscope is passed through the mouth or nose into the lungs and fluid is squirted into a small part of the lung and then recollected for examination. A BAL sample (minimal 30 mL) will be obtained from upper and lower lobes using conventional techniques. The following research investigations will be performed: Luminex cytokine arrays, flow Cytometry, gene expression profiles, examination of proliferative, cytotoxic, and apoptotic response of BAL lymphocytes to 3rd party epithelial cells and allogeneic lymphocyte population, and T regulatory cell quantification by real time PCR using primers to fox p3.

8.3 High Resolution Chest CT

HRCT is performed using a conventional CT scanner. However, imaging parameters are chosen so as to maximize spatial resolution:

- A narrow slice width is used (usually 1-2 mm)
- A high spatial resolution image reconstruction algorithm is used
- Field of view is minimized, so as to minimize the size of each pixel
- Other scan factors (e.g. focal spot) may be optimized for resolution at the expense of scan speed

As HRCT's aim is to assess a generalized lung disease, the test is conventionally performed by taking thin sections 10-40 mm apart. The result is a few images which should be representative of the lungs in general, but which cover only approximately one tenth of the lungs.

Intravenous contrast agents are not used for HRCT as the lung inherently has very high contrast (soft tissue against air).

8.4 Six Minute Walk Test

The six-minute walk test is generally used at the start of a Pulmonary Rehabilitation program and/or in the evaluation of lung transplant and will be used in this study to evaluate the primary endpoint, which is change in BO status. The object of this test is to walk on a flat surface such as a hallway for 6 minutes during which time subjects will be asked to rate their degree of breathlessness and fatigue levels. The distance walked during the 6 minutes is measured.

Blood pressure, heart rate, respiratory rate, and resting blood saturation by pulse oximetry will be taken after the test. Oxygen saturation will be taken during the walk. Subjects will be asked to assess their breathing status using a 0-10 scale.

Subjects will be instructed to:

- Wear comfortable clothing
- Wear shoes that are comfortable to walk in, such as tennis shoes.
- Take their medications as prescribed.
- Eat a light meal before early morning or early afternoon tests.
- Not to exercise vigorously within 2 hours of beginning the test.

8.5 Quality of Life Measurements

Participants sixteen years and older that speak English will perform self-report questionnaires using the SF36, Human Activity Profile (HAP), Chronic Respiratory Disease Questionnaire Self-Administered Standardized CRQ-SAS), and a GVHD questionnaire. These assessments will occur at the week 70 assessment and at end of study assessment.

- The SF36 is a 36 item self-report questionnaire that measures the impact of physical and emotional health status on functional performance. It has been used extensively, and is accepted by the U.S. Food and Drug Administration as proof of therapeutic benefit for improved functioning and other patient-reported outcomes.
- The HAP is a 94-item questionnaire that assesses the frequency with which individuals perform common activities.
- The CRQ-SAS is a 20-item questionnaire that assesses dyspnea, fatigue, emotional functioning, and mastery.
- A GVHD questionnaire (PBSC transplant patients, group A) designed by Lee and colleagues is a 30-item symptom scale with seven subscales to capture cGVHD symptom burden.

9.0 ANCILLARY LABORATORY RESEARCH STUDIES

9.1 Sample Collection: During the course of this study, blood and bronchoalveolar lavage samples will be collected for correlative laboratory research studies.

9.2 Intended use: These specimens will not be used for diagnostic purposes. Studies conducted on these samples will not be used in assessing the primary endpoint but are undertaken for secondary endpoints (Tissue pathogenesis of BO as detailed below) and/or exploratory ancillary research, which are approved by the NHLBI IRB and listed in Appendix B of the protocol. As these tests are being performed for secondary or exploratory purposes, failure to obtain the tests will not be considered a protocol deviation.

9.2.1 Multiplex cytokine arrays

Biopsies, BAL, and peripheral blood samples will be prepared for multiplex cytokine array analysis. Multiplex bead arrays allow one to independently and quantitatively assay multiple analytes simultaneously in small volumes of material.

9.2.2 Flow Cytometry

BAL and peripheral blood samples will be prepared for analysis using flow cytometry. Samples will be analyzed for T cell, NK cell and neutrophils expression.

9.2.3 Gene expression profiling

BAL, and peripheral blood samples will be prepared for the gene array analysis. Specifically, arrays focused on Apoptosis, Dendritic cells/Antigen Presentation, Cytokines,

and Chemokines/Adhesion Molecules will be used. The use of smaller, more focused arrays decreases statistical problems associated with multiple testing and simplifies data analysis. Most interesting and significant findings will be validated by PCR and protein based assays such as immunohistochemistry and ELISA.

9.3 Storage: Research samples will be stored in the secure laboratory of [name] (NHLBI) and/or [name] (Clinical Center/Critical Care Medicine Department) under the care and supervision of the principal investigator of this study. All laboratory personnel with access to samples or patient information will complete the NIH online course in Protection of Human Subjects. Efforts to ensure protection of patient information include:

- The laboratory is located in a controlled access building and laboratory doors are kept locked at all times. Visitors to the laboratory are required to be accompanied by laboratory staff at all times.
- Hard copy records or electronic copies of documents containing patient information are kept in the locked laboratory or other controlled access locations.
- An electronic database is used to store information related to patient samples processed by the laboratory.
- All samples collected will be assigned a unique code.
- Vials holding patient samples are labeled with the sequential laboratory accession ID number that does not contain any personal identifier information.
- Samples will be stored until they are no longer of scientific value or until the patient withdraws consent, at which time they will be destroyed.
- If a patient withdraws consent for their continued use, their sample will be destroyed.

9.4 Tracking: Samples will be ordered and tracked through the CRIS Research Screens. Should a CRIS screen not be available, the NIH form 2803-1 will be completed and will accompany the specimen and be filed in the medical record. Samples will not be sent outside NIH without IRB notification and an executed MTA.

9.5 End of study procedures: Samples from consenting subjects will be stored until they are no longer of scientific value or if a subject withdraws consent for their continued use, at which time they will be destroyed. The results will be submitted to the clinicaltrials.gov database.

9.6 Loss or destruction of samples: Should we become aware that a major breach in our plan for tracking and storage of samples has occurred, the IRB will be notified.

10.0 BIOSTATISTICAL CONSIDERATIONS

10.1 Primary and secondary endpoints

The *primary objective* is to assess the long-term safety and efficacy of continued therapy with inhaled aerosolized cyclosporine A solution in hematopoietic (group A) and lung transplant patients (group B) with bronchiolitis obliterans (BO) or BO syndrome (BOS) who have shown evidence for a benefit of CIS as previously defined.

Secondary objectives include investigation of the inflammatory pathways that lead to chronic BO and ascertainment of the long term anti-inflammatory effects of this CSA preparation ex vivo and in vivo. *Secondary endpoints* include improvement of high-resolution CT images, the results of peripheral

blood and bronchoalveolar cytokine arrays (secondary markers of inflammation), and the results of functional capacity measurements (pulmonary function tests), and quality of life measurements.

We will evaluate response for group A and group B patients separately, in order to assess if the treatment is effective in each disease.

Note: As of March 2017 this study is no longer enrolling lung transplant recipients.

10.2 Sample size

As this is an extension study, the number of patients to be included is directly determined by the number of patients having successfully completed the end of the End of Study (Week 18) visit on companion initial treatment protocol (Phase II Trial of Cyclosporine Inhalation Solution (CIS) in Lung Transplant and Hematopoietic Stem Cell Transplant Recipients for Treatment of Bronchiolitis Obliterans) without evidence of progression of BO. The number cannot exceed 78.

10.3 Data Analyses

Any patient who receives any amount of study medication during this extension study will be considered evaluable for safety analysis. Adverse events will be tabulated by severity and disease (lung versus hematopoietic).

Final statistical analysis of efficacy will be performed once all subjects have completed the end of study assessments and all data have been archived for analysis. We will use stratified analyses to account for effects of systemic immunosuppressive agents and other prognostic factors.

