2.6.4 Previous Human Experience

The systemic toxicity of cyclosporine has been well characterized in humans and animals. The most common toxicities associated with systemic exposures include renal dysfunction, hypertension, dyslipidemia, hirsutism, headache, increased risk of infections, and tremor. Additional, less common toxicities include gum hyperplasia, hyperkalemia, thrombocytopenia, and seizure. Hypertension, dyslipidemia, and renal dysfunction are particularly prevalent in the lung transplant population with extended use.

As cyclosporine is partially systemically absorbed following inhalation, the risk of systemic toxicities in addition to the risk of local respiratory tract toxicities was evaluated in repeat dose animal studies. After demonstrating efficacy in preclinical canine and rodent transplant models, ethanol-based inhaled cyclosporine was tested in a series of open-label protocols evaluating its safety and efficacy in lung transplant recipients with established BO and/or refractory acute rejection (AR). In patients with established BO, the administration of inhaled cyclosporine in conjunction with standard immunosuppressive therapy led to improvement in rejection histology, stabilization of pulmonary function, and improvement in survival compared to contemporary and historical controls^(15,16). In patients with AR that failed to respond to high-dose pulsed methylprednisolone, the administration of inhaled cyclosporine in conjunction with standard immunosuppressive therapy led to improvement in AR histology, improvement in pulmonary function, a decline in pro-inflammatory cytokine production in bronchoalveolar samples, and improvement in survival compared to contemporary control patients^(17,18,19). Although these studies demonstrated the safety of inhaled cyclosporine, the ethanol solvent was associated with substantial respiratory tract irritation and was subsequently changed to propylene glycol.

These open label protocols were followed by a randomized, double-blind, placebo-controlled study of CIS designed to test the efficacy of CIS in preventing lung allograft rejection and improving outcomes when given as prophylactic therapy⁽⁸⁾. A total of 56 patients were enrolled within 7 to 42 days following their single- or double-lung transplant and treated with either CIS or placebo

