7.0 CLINICAL MONITORING PLAN

Human Biologic materials will be collected as follows for the clinical evaluation and management of the patient. Samples will be ordered and tracked through the CRIS screens. Should a CRIS screen not be available, the NIH form 2803-1 will be completed and will accompany the specimen and be filed in the medical record.

7.1 On study assessments: Subjects will be asked to return to the NIH Clinical Center the end of Week 24, 30, 36, 42, 48, 54, 60 (+/- 7 days) for the following assessments:

- Interim assessment with emphasis on symptomatology
- Vital signs
- ECOG performance status
- Review of concomitant medications and adherence
- CBC with differential (when possible, done concurrently with post transplant monitoring)
- Acute Care, Mineral and Hepatic Panels (when possible done concurrently with post transplant monitoring)
- Plasma cyclosporine level
- Peripheral blood samples
- Repeat Serum Beta- HCG in women of childbearing potential
- Pulmonary Function tests
 - Forced Spirometry
 - Slow Spirometry
 - Lung volumes with nitrogen washout
 - Single Breath Diffusion
 - Six minute walk test
 - Exhaled Nitric Oxide measurement (in a subset of subjects)
 - Review of Peak Flow measurements
- Bronchoscopy and bronchoalveolar lavage (BAL) (Weeks 30, 42, 54 only)*
BAL to be analyzed by
 - Luminex cytokine arrays
 - Flow Cytometry
 - Gene expression profiles

- Proliferative, cytotoxic, and apoptotic response of BAL lymphocytes to 3rd party epithelial cells and allogeneic lymphocyte population
- T regulatory cell quantification by real time PCR
- High Resolution Chest CT (weeks 30, 42, 54 only)*

* Bronchoscopy and High-resolution CT scans are optional unless clinically indicated.

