7.2 End of week 70 and end of study assessments

Patients will be monitored at week 70 (+/- 1 week) and at end of study participation with the following assessments:

- Assessment with emphasis on symptomatology
- Vital signs
- ECOG performance status
- Review of concomitant medications and compliance
- CBC with differential (if possible, done concurrent with post transplant monitoring)
- Acute Care, Mineral and Hepatic Panels (if possible, done concurrently with post transplant monitoring)
- Plasma cyclosporine level
- Repeat Serum Beta- HCG in women of childbearing potential
- Pulmonary Function tests
 - Forced Spirometry
 - Slow Spirometry
 - Lung volumes with nitrogen washout
 - Single Breath Diffusion
 - Six minute walk test
 - Exhaled Nitric Oxide measurement (in a subset of subjects)
 - Review Peak Flow measurements
- Bronchoscopy and bronchoalveolar lavage (BAL)*
 - Luminex cytokine arrays
 - Flow Cytometry
 - Gene expression profiles
 - Proliferative, cytotoxic, and apoptotic response of BAL lymphocytes to 3rd party epithelial cells and allogeneic lymphocyte population
 - T regulatory cell quantification by real time PCR using primers to fox p3
- Peripheral blood samples
- High Resolution Chest CT*
- Quality of life assessments
 - SF36
 - GVHD questionnaire (PBST transplant patients only)
 - HAP Questionnaire
 - CRQ-SAS questionnaire
 - Comfort of study drug administration

* Bronchoscopy and High-resolution CT scans are optional unless clinically indicated.

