13.3 Risks and Discomforts

13.3.1 Related to Inhaled CIS

CIS is under development for the indication of improved BOS-free survival following lung transplantation. As of November 13, 2009, approximately 444 lung transplant recipients have received CIS under protocols ACS001, ACS002, ACS004, or CIS001. In ACS001, the following adverse events occurred significantly more often in patients receiving CIS than in patients receiving placebo:

- Events that occurred in 30 to 50% of patients receiving CIS: cough, chest pain, back pain, increased urinary frequency, pharyngitis, exacerbation of shortness of breath, and lung consolidation.
- Events that occurred in 10 to 29 % of patients receiving CIS: cardiac murmur, respiratory tract irritation, polyuria, somnolence, hyperlipidemia, respiratory disorder, and hemoptysis.

In the studies that were not placebo controlled, or are as yet unblinded, the following adverse events were seen:

- Events that occurred in greater than 10% of patients: pyrexia, nausea, diarrhea, dyspnea, cough, wheezing, chest pain, pharyngitis, renal impairment, peripheral edema, lung transplant rejection, headache, insomnia, and neutropenia.

- Events that occurred in 5 to 10% of patients: Pharyngolaryngeal pain, pleural effusion, rhinorrhea, constipation, vomiting, fatigue, chest pain, candidiasis, pseudomonas infection, sinusitis, pneumonia, hyperkalemia, leucopenia, anemia, and hypertension.

Although not previously observed, in the initial phase of the NIH study, one subject did develop a rib fracture associated with coughing.

Unknown side effects: In addition, as with other clinical studies using experimental medicines and in subjects with serious medical conditions, there may be adverse events or side effects that are currently unknown and certain of these unknown risks could be permanent, severe, or life threatening. Subjects will therefore be carefully monitored and instructed to seek medical attention in the event of severe adverse events and contact the research team as needed.

Cyclosporine, when taken by mouth can cause kidney damage especially if blood levels are high. So far, use of CIS has not caused this problem in previous human research studies and should not increase this risk since blood levels have been very low.

APT Pharmaceuticals remains attentive to safety throughout all ongoing studies. Additional unexpected safety findings will be provided to investigators upon receipt and evaluation.

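### No lipid test is scheduled although the plan reports excess hyperlipidemia on CIS, and the only safety analysis is an attribution-filtered adverse-event table, so hyperlipidemia would be captured only incidentally

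*Combined protocol and SAP*

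**What the plan says.** **Objective and analysis.** Sections 1.1 and 10.1 make long-term safety part of the primary objective. The only safety analysis in section 10.3 is "Adverse events will be tabulated by severity and disease (lung versus hematopoietic". No summary of laboratory values, vital signs or concomitant drugs is planned.

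**Known harms.** Section 13.3.1 introduces its first list with "In ACS001, the following adverse events occurred significantly more often in patients receiving CIS than in patients receiving placebo". One entry reads "Events that occurred in 10 to 29 % of patients receiving CIS: cardiac murmur, respiratory tract irritation, polyuria, somnolence, hyperlipidemia, respiratory disorder, and hemoptysis". Hypertension appears elsewhere in that section, at 5 to 10%, in a list that ends "candidiasis, pseudomonas infection, sinusitis, pneumonia, hyperkalemia, leucopenia, anemia, and hypertension". That list covers studies without a placebo control or described as not yet unblinded. Section 2.6.4 says of cyclosporine that "Hypertension, dyslipidemia, and renal dysfunction are particularly prevalent in the lung transplant population with extended use".

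**Measurement.** The laboratory tests at weeks 24 to 60 (section 7.1) are a blood count, "Acute Care, Mineral and Hepatic Panels (when possible done concurrently with post transplant monitoring"), a plasma cyclosporine level and a pregnancy test. Section 7.2 repeats these at week 70 and end of study. Section 7.3 adds routine assessment, physical examination and lung function every 6 to 12 weeks thereafter. Vital signs are on the lists in 7.1 and 7.2, as is a concomitant-drug review (in 7.2, "Review of concomitant medications and compliance").

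**What counts as an event.** Section 12.1 defines an adverse event broadly enough to include an abnormal sign. Section 12.3 narrows collection: a laboratory event must be a progression to grade 3 or 4 from the pre-dose assessment. Clinical events and abnormal laboratory results judged directly attributable to the transplant, to post-transplant drugs or to progression of the underlying disease go to the medical record only.

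**The concern.** An adverse-event table can show only what someone looked for and then chose to file. Hyperlipidemia usually has no symptoms, so without a scheduled test it comes to light only if another physician orders one. If a value does turn up, it must reach grade 3 or 4 and must not be put down to the patient's other drugs. Many of these patients will be on systemic immunosuppressants that also raise lipids and blood pressure, so attribution to those drugs is an easy and often reasonable judgement.

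The safety report could then show little or no hyperlipidemia after long exposure, and that could be taken as reassurance about an event the plan itself reports in excess over placebo. The plan's background makes the question a live one. Section 2.6.4 reports that long-term CIS did not worsen the known toxicities of systemic cyclosporine, while section 13.3.1 reports excess hyperlipidemia. A long-term extension could inform that tension, but as written it would not.

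**Working it through.** No sample size, power or event figure in the plan is at issue, so there is nothing to reproduce. The check sets the sections side by side.

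**Step 1: is a lipid test scheduled?**

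| Time point | Section | Laboratory tests named | Lipid test named |
|---|---|---|---|
| Weeks 24, 30, 36, 42, 48, 54, 60 | 7.1 | blood count; acute care, mineral and hepatic panels; cyclosporine level; beta-HCG | no |
| Week 70 and end of study | 7.2 | same | no |
| After week 70 | 7.3 | none specified | no |

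That is 7 + 1 = 8 scheduled visits to week 70 with no named lipid measurement. The contents of the panels are not given, so this assumes they include none. Section 7.4 lets long-distance subjects attend at 12- or 24-week intervals after week 30, so some would have fewer than 8 visits.

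**Step 2: how could hyperlipidemia reach the table in 10.3?** There are two routes. One is a value forwarded by a home physician, since section 11.1 says such values are entered. The other is a clinical diagnosis recorded as an event under 12.1. Both are unscheduled, and both pass through 12.3. A laboratory change needs grade 3 or 4 relative to a pre-dose assessment, and either route is closed if the event is attributed to the transplant or post-transplant drugs.

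**Step 3: how could a blood-pressure rise reach the table?** Blood pressure is measured: vital signs are listed in 7.1 and 7.2, and section 8.4 names blood pressure at the six-minute walk. Raised pressure can be recorded as an event (12.1), graded (12.2) and tabulated (10.3). It is subject to the same attribution rule in 12.3, and no summary of the values themselves is planned.

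**Step 4: illustration of size.** Inputs are the bands in 13.3.1 and the ceiling of 39 per group. Expected count = N × rate; P(at least one) = 1 − (1 − rate)^N.

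- Hyperlipidemia: 39 × 0.10 = 3.9; 39 × 0.29 = 11.3. P(at least one) is 1 − 0.90^39 = 0.984 at the lower rate, and higher above it.
- Hypertension: 39 × 0.05 = 1.95; 39 × 0.10 = 3.9. P(at least one) runs from 1 − 0.95^39 = 0.865 to 0.984.

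These figures assume that the bands from lung recipients apply to this population and follow-up. They show that a zero count would be surprising if capture were complete. They do not predict how many cases CIS will cause.

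**The case against.** The other side has several good points.

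- **A reader might infer that lipids are never measured.** The documents do not show this. Panel contents are not listed, and home-physician values are entered (11.1). They support only that no lipid test is scheduled.
- **A reader might infer that two harms would be missed.** For hypertension this is wrong: pressure is taken, and a rise can be recorded, graded and tabulated. What is lacking is a summary of the values, and protection against the attribution rule in 12.3.
- **A reader might infer that both are established long-term harms of inhaled CIS.** The extended-use sentence in 2.6.4 closes a paragraph on systemic cyclosporine. Section 2.8 puts systemic exposure from CIS about 7-fold below oral dosing. Section 2.6.4 also reports no worsening of known toxicities on long-term CIS, although the examples it names do not include lipids or blood pressure. Only hyperlipidemia has a stated excess over placebo.
- **The rate is weak evidence of size.** The 10 to 29% is a total rate in lung recipients with no placebo rate beside it, so no CIS-attributable number follows. Subjects here have already been treated on the initial protocol, so some cases would precede entry.
- **Existing data have limits.** The extension baseline is already on treatment, and the baseline column of the section 4.0 schedule does not list vital signs. Section 11.1 describes abstraction from progress notes; it does not say that drug starts or pressures are already in the database.
- **Timing.** Section 13.4.1 says that, as of May 10, 2019, the study is closed to accrual and continues only in data and/or sample analysis. A call for prospective lipid testing would probably be moot.

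All of these stand as limits on the point. None supplies scheduled lipid ascertainment or an analysis free of the 12.3 filter.

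**Conclusion.** The point holds in a limited form. An event with a stated excess over placebo has no scheduled measurement, and the single safety analysis depends on events filtered by grade and attribution. Followed as written, the plan would capture hyperlipidemia only incidentally, so a low count would be uninformative. For blood pressure the gap is smaller: the data are taken, but they enter the analysis only as attribution-filtered events.

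The conclusion assumes that the named panels contain no lipid test and that 12.3 governs what 10.3 tabulates. The range of 3.9 to 11.3 in 39 is illustrative and assumes that the lung-recipient rate carries over; the documents give no rate for stem cell recipients. This is a worthwhile, inexpensive improvement to the safety report. It does not show that the study has missed a harm or that CIS causes one here.

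**What to change.** Add to section 10.3 a descriptive safety summary from existing records, by group and regardless of attribution:

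1. The number of subjects who start or increase a lipid-lowering or antihypertensive drug after the extension baseline, from the concomitant-drug reviews and abstracted notes.
2. Change in systolic and diastolic pressure from the first available extension value, by visit, with the number observed at each visit and a note that this baseline is already on CIS.
3. Any lipid values in NIH or home-physician records, with the number of subjects who have none.

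State in the report that lipids were not measured on schedule, so an absence of hyperlipidemia is not evidence of safety.

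No visit, procedure or test is added. The cost is some record abstraction, a few tables and a sentence or two of text. Drug starts are an imperfect proxy, and steroids and oral calcineurin inhibitors confound both lipids and pressure in a study without a control arm. The summaries should therefore be presented as descriptive only.
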